Removal of Hardware		X	X	X	X	X	X
Adverse Event	X	X	X	X	X	X	X
End of Study							X

Criteria for Removal of Hardware

Hardware may be removed if there is a surgical indication or patient/surgeon preference for removal. Patients will be asked whether they feel bothersome sensitivity at the both medial and lateral malleolus. If they mention sensitivity to light touch that is not bothersome they should not be subjected to hardware removal unless by patient or surgeon preference and noted as medial or lateral hardware removed for preference. On the other hand, if they mention bothersome sensitivity, it would be rated on a 0-5 Likert intensity scale. All bothersome sensation will be subjected to hardware removal and noted as removal for sensitivity. Other reasons for hardware removal indications include infection and non-union or mal-union requiring revision open reduction and internal fixation. The location of symptoms and reason for hardware removal should be specified and documented.

Documentation of Fracture Union

Union will be defined as a pain free fracture site on examination with evidence of radiographic healing and a return to full weight bearing confirmed by the operating surgeon

Power Analysis and Statistics

Retrospective review of ankle hardware removal cases indicates that 6% (8/126) of patients have their hardware removed for non-pain issues (e.g., infection, etc.) at 6 months and 17% (22/126) of patients have their hardware removed for pain on the medial or lateral side of the ankle at 6 months.⁸ Hence, the overall rate of hardware removal is 24% but if we can reduce half of the medial hardware removals the overall rate would be 14.5%. To detect this 9.5% difference, it would take 424 randomized patients (alpha = 0.05, and 80% power). Medial hardware removal will be prohibited for lateral hardware pain.

Utilizing the STRIDE database available at Stanford University, there have been 155 procedures involving fixation of the medial malleolus (CPT: 27766, 27814, 27822, 27823) over the past three years. Assuming a similar procedure burden at the other major Level I Trauma center and extrapolating this three-year data, we estimate the capability to enroll 500 patients over three years.

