All continuous variables will be reported as the mean and errors are reported as standard deviation. All categorical variables will be reported as the subset number and percentage of the total. Comparisons will be performed with the appropriate statistical test when indicated. Statistical significance will be set at p less than 0.05 with an appropriate Bonferroni correction for multiple comparisons when indicated.

Budget

The vast majority of the budget will go toward an experienced fulltime clinical research coordinator, level II (CRCII, Table 2). This person is critical to our success. Appropriately, some funds will be devoted to insuring the proper training and certification for the CRCII involved in this project as well as supply adequate computing power and meet secure data storage needs. Some funds would be used by the principal investigator and co-investigators to offset local travel and travel to national and international meetings to present the findings of this interdisciplinary work, including the American Academy of Orthopaedic Surgeons (AAOS), the Orthopaedic Trauma Association (OTA), and the American Orthopaedic Foot and Ankle Society (AOFAS).

Table 2: General Budget

Expense			Effort	Cost
Personnel	Principal Investigator	[name]	10%	\$36,000/year
	Co-Investigator	[name]	3%	\$10,000/year
	Co-Investigator	[name]	3%	\$10,000/year
	Co-Investigator	[name]	3%	\$10,000/year
	Co-Investigator	[name]	3%	\$10,000/year
	Co-Investigator	[name]	3%	\$10,000/year
	CRCII	TBD: Stanford	100%	\$90,000/year

	CRCII	TBD: 3 rd center	75%	\$68,000/year
	CRCII	TBD: Kaiser	75%	\$68,000/year
Equipment	Computers			\$3,000/year
	Secure Storage			\$1,000/year
Training				\$5,000/year
Travel	Society Meetings			\$5,000/year
	Between Sites			\$5,000/year
				\$275,000/year

Acumed Study Summary	
Company	Stanford University
Title	Prospective, multi-center, randomized, controlled study evaluating the union rate, rate of medial malleolus hardware removal and clinical outcomes after medial malleolus fracture fixation with Acutrak headless compression screws
Short Title	Acutrak Fixation of Medial Malleolus Fractures
Protocol Number	
Treatment Device	Acutrak headless compression screws
Control Device(s)	Mini-fragment Plating, Antiglides Plating, Headed Unicortical Screws, Headed Bicortical Screws, Tension Band Wiring

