Intended Use	The Acutrak headless compression screws are intended to provide fixation and anatomically reduce fractures of the medial malleolus that occur via supination-external rotation, pronation-external rotation, or pronation-abduction resulting in an oblique fracture pattern as well as supination-adduction resulting in a vertical shear fracture pattern.
Study Purpose	The fixation provided by the Acutrak headless compression screws provide sufficient fixation to achieve union and a favorable clinical outcome in both horizontal and vertical medial malleolus fractures when compared to bicortical and unicortical screw fixation, tension band wiring, and mini-fragment or buttress plating. However, minimizing the amount of dissection required for implantation as well as lack of prominent hardware surfaces will reduce the incidence and severity of hardware related pain and correspondingly the necessity of hardware removal.
Study Objectives	
Primary:
 
 • A successful outcome would be a reduction in the rate or severity of hardware related pain localized to the medial malleolus reducing the incidence of hardware removal from the medial malleolus at one year after sustaining an ankle fracture.
	
Secondary:
 
 • Another successful outcome would be an equivalent radiographic and clinical union rate when compared to traditional fixation methods. • Another successful outcome would be an equivalent PROMIS scores when compared to traditional fixation methods.

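### The 424-patient, 80% power statement is for overall hardware removal at 6-month rates, not the medial one-year primary objective; as written it holds only one-sided, on a difference that appears inflated by rounding

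*Combined protocol and SAP*

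**What the plan says.** **Primary objective** (Acumed Study Summary, Study Objectives). Success is a reduction in the rate or severity of pain at the medial malleolus, "reducing the incidence of hardware removal from the medial malleolus at one year after sustaining an ankle fracture". The study title in the same summary also names the "rate of medial malleolus hardware removal and clinical outcomes after medial malleolus fracture fixation".

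**Aims.** Aim 4 (Specific Aims, repeated under Safety Objective in the Study Summary) seeks superiority on hardware removal, without giving a side or a time point.

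**Sample size** (Power Analysis and Statistics). The source is a retrospective series in which "6% (8/126) of patients have their hardware removed for non-pain issues" and "17% (22/126) of patients have their hardware removed for pain on the medial or lateral side of the ankle at 6 months"; the first figure is also at 6 months. The section puts overall removal at 24% and says "if we can reduce half of the medial hardware removals the overall rate would be 14.5" per cent. It continues: "To detect this 9.5% difference, it would take 424 randomized patients (alpha = 0.05, and 80% power"). It adds that "Medial hardware removal will be prohibited for lateral hardware pain", and on capacity that "we estimate the capability to enroll 500 patients over three years".

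**Testing.** The statistical paragraph after the power section and the Study Summary's Statistical Methods set significance at p below 0.05 and leave the choice of test open. Neither says one-sided or two-sided. No allocation ratio, loss to follow-up, medial-only rate or one-year rate is given.

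**The concern.** The power calculation and the primary objective differ in side (any against medial) and in time (6 months against one year). The objective also joins pain with removal and does not say which is tested. Aim 4 could be read either way. The documents therefore leave the primary comparison open, and the only sample-size justification belongs to one version of it.

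Two things are at stake. First, the choice of overall or medial removal, of time point and of sidedness could be made after the data are seen, and each can change the conclusion. Second, the 80% figure gives an assurance that has not been established for the stated objective. If overall removal is analysed, removals that a medial implant is not expected to affect dilute the contrast. If medial removal is analysed, the power depends on a control rate that the documents do not supply.

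**Working it through.** **Inputs.** From Power Analysis and Statistics: 24% and 14.5%; alpha 0.05; power 80%; N = 424; capacity 500; counts 8/126 and 22/126. Assumed: 1:1 allocation (212 or 250 per arm) and no loss to follow-up.

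**Formulas** (pooled-variance comparison of two proportions, no continuity correction), with p̄ = (p1 + p2)/2:

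- n per arm = [z_α √(2p̄(1−p̄)) + z_β √(p1(1−p1) + p2(1−p2))]² / (p1 − p2)²
- power = Φ{[(p1 − p2)√n − z_α √(2p̄(1−p̄))] / √(p1(1−p1) + p2(1−p2))}

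**Step 1: reproduce 424.** With p1 = 0.24 and p2 = 0.145, p̄ = 0.1925 and the two square roots are 0.5576 and 0.5535.

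- One-sided (z_α = 1.645, z_β = 0.842): n = 211.9, so 212 per arm and N = 424, an exact match.
- Two-sided (z_α = 1.960): n = 269.2, so 270 per arm and N = 540. Power is 70.0% at 424 and 77.0% at 500.

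Unpooled-variance and arcsine versions of the two-sided test both need 534, so the choice of formula does not close the gap.

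**Step 2: where 14.5% comes from.** The protocol does not show the derivation, but its rounded parts give the figure exactly: 6% + 17%/2 = 6% + 8.5% = 14.5%. This halves all pain removals, although the source describes them as medial or lateral, and leaves non-pain removals unchanged. The same rounded parts sum to 6% + 17% = 23%, whereas the 24% is (8 + 22)/126 = 30/126 = 23.8%, rounded up. Taking 14.5 from 24 gives 9.5 points; taking it from 23 gives 8.5.

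**Step 3: redo it on the counts.** Halving 22 pain removals leaves 8 + 11 = 19, so the comparison is 30/126 = 23.8% against 19/126 = 15.1%, a drop of 11/126 = 8.7 points. Here p̄ = 0.1944 and the square roots are 0.5597 and 0.5563.

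| Comparison of overall removal | N for 80%, one-sided | N for 80%, two-sided | Power at 424, one-sided | Power at 424, two-sided |
|---|---|---|---|---|
| 24% vs 14.5% (as written) | 424 | 540 | 80% | 70% |
| 30/126 vs 19/126 (counts) | 508 | 644 | 74% | 62% |

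**Step 4: the medial endpoint.** No medial rate is given, so every control rate below is an assumption, halved under treatment and tested two-sided at 0.05. The 8.7% row is 11/126, the rate if half of the 22 pain removals were medial.

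| Assumed medial control rate | N for 80% | Power at 424 |
|---|---|---|
| 19% | 424 | 80% |
| 17.5% | 466 | 76% |
| 15% | 556 | 69% |
| 12% | 712 | 58% |
| 8.7% | 1,010 | 44% |

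A higher rate works the other way: an assumed 22% gives 87% at 424. Removals accumulate, so a one-year rate above the 6-month rate would raise power if the relative effect holds.

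**The case against.** The strongest reply is that the medial side is plainly the target. The title says so, the power section speaks of halving medial removals, and medial removal for lateral pain is barred. If 9.5 points is half of the medial removals, the medial control rate is 2 × 9.5 = 19%, and 19% against 9.5% needs exactly 424 patients two-sided (80.1% power). A reader might infer that the sample size is right and only the wording is loose.

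Part of this stands: 424 should not be called an arithmetic error, because it fits a conventional calculation. But 19% appears nowhere in the documents. It corresponds to 0.19 × 126 = 23.9, about 24 of the 30 removals, which is more than the 22 removed for pain on both sides together. The derivation 6% + 8.5% reproduces 14.5% without it, so the match at 424 may be coincidence. It is one possible reading, and it is still based on 6-month data.

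A second reply is that overall removal is not foreign to the plan, since aim 4 names no side. That is fair. The accurate description is that the aims, the power section and the primary objective do not agree, rather than that the power section used an endpoint from nowhere.

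A third is that no passage promises a two-sided test and the aims are directional. That is also true. The 70% and 62% figures depend on applying the conventional two-sided standard; the protocol does not state it. Even one-sided, however, the source counts give 74%, not 80%.

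**Conclusion.** The concern holds. The stated 80% at 424 is not the power for the stated primary objective, and it is not reached on the protocol's own counts. For overall removal as written, power is 80% one-sided and 70% two-sided; on the counts it is 74% and 62%. For medial removal at one year, power cannot be determined from the documents.

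A reader might go further and conclude that the trial is underpowered for its primary objective. The documents do not support that. A one-year medial rate of 19% or more, if halved, would give at least 80% two-sided at 424, while lower rates would not. The 80% is unsupported, not shown to be too high.

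These figures assume 1:1 allocation, no loss to follow-up and a halving of the relevant rate. The explanation of 14.5% in Step 2 is an inference: it matches exactly, but the protocol does not state it.

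**What to change.** 1. Name one primary endpoint that matches the primary objective, for example medial malleolus hardware removal by one year (yes/no). State which reasons for removal count, using the location and reason that the protocol already requires to be recorded. Make overall removal and pain severity secondary.
2. State a two-sided 0.05 test.
3. Correct the 24% and 14.5% arithmetic so that both rates come from the same counts, and show the derivation.
4. Restate power at the planned size for the named endpoint. Use an explicit medial one-year control rate, either sourced or labelled as an assumption, and show a range that includes rates below 15%.
5. Use the same side and time wording in the Specific Aims, the power section, and both the Study Objectives and the Safety Objective of the Study Summary.

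The cost is protocol wording and a recalculation. No new data fields are needed: reason and location are already recorded, and removal is already captured at the one-year contact in Table 1. The medial one-year rate must be found or assumed openly. The downside is that the restated power may fall below 80%; the fix itself does not require a larger sample.
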